5. SUBJECT ENROLLMENT

Before subjects begin participation in any study-specific activities/procedures, Amgen requires a copy of the site's written institutional review board/independent ethics committee (IRB/IEC) approval of the protocol, informed consent form, and all other subject information and/or recruitment material, if applicable (see [Section 11.2](#)).

Subjects must personally sign and date the IRB/IEC and Amgen approved informed consent form before commencement of study-specific activities/procedures.

Upon completion of the screening period the subject is evaluated by the investigator and providing the subject continues to meet the inclusion/exclusion criteria, the subject is subsequently eligible to be enrolled in the study and either randomized or assigned to a treatment regimen.

A subject is considered enrolled when the investigator decides that the subject has met all eligibility criteria. The investigator is to document this decision and date, in the subject's medical record and in/on the enrollment case report form (CRF).

Each subject who enters into the 14-day screening period for the study receives a unique subject identification number before any study-related activities/procedures are performed. The subject identification number will be assigned by IVR/IWR. This number will be used to identify the subject throughout the clinical study and must be used on all study documentation related to that subject. This number will not necessarily be the same as the randomization number assigned for the study. If a subject has not met all eligibility criteria at the end of the 14-day window, the subject will be registered as a screen fail. Screen failed subjects may be eligible for re-screening once.

The subject identification number must remain constant throughout the entire clinical study; it must not be changed after initial assignment, including if a subject is rescreened.

5.1 Randomization/Treatment Assignment

Subjects will be randomized in a 1:1 ratio to receive each etanercept formulation in 1 of 2 crossover treatment sequences and will be stratified by indication. Subjects randomized to the first treatment sequence (ie, sequence AB) will receive 1 dose of the current formulation (ie, treatment A) during the first study period, followed by a second visit 1, week later during the second study period at which time subjects will receive 1 dose of the modified formulation (ie, treatment B). Subjects randomized to the second treatment sequence will undergo the same procedures but will receive investigational product in the opposite order (ie, sequence BA). At each study visit, subjects will inject the blinded treatment and immediately (ie, within 30 seconds of injection) record the associated injection site pain using the VAS.

The randomization will be performed via IVR/IWR system on-study day 1.

The randomization date is to be documented in the subject's medical record and on the enrollment CRF.

5.2 Site Personnel Access to Individual Treatment Assignments

A subject's treatment assignment should only be unblinded when knowledge of the treatment is essential for the further management of the subject on this study.

Unblinding at the study site for any other reason will be considered a protocol deviation. The investigator is strongly encouraged to contact the Amgen Clinical Trial Manager before unblinding any subject's treatment assignment, but must do so within 1 working day after the event (ie, unblinding).

6. TREATMENT PROCEDURES

6.1 Classification of Products and/or Medical Devices

The Amgen Investigational Products used in this study includes etanercept and SureClick auto injector device.

Note: Non-investigational medical device(s) (ie, medical device[s]not under study) or products will be described in [Section 6.5](#).

The Investigational Product Instruction Manual, a document external to this protocol, contains detailed information regarding the storage, preparation, destruction, and administration of etanercept.

6.2 Investigational Product

6.2.1 Amgen Investigational Product Etanercept

Etanercept will be manufactured and packaged by Amgen Inc. and distributed using Amgen clinical study drug distribution procedures. The solution of etanercept is clear and colorless. Etanercept will be supplied in a single-use SureClick autoinjector as a sterile, preservative-free solution for subcutaneous injection. Each single-use SureClick autoinjector contains 0.98 mL of 50 mg/mL etanercept in either the currently marketed formulation (Treatment A) or a modified formulation (Treatment B).

6.2.1.1 Dosage, Administration, and Schedule

All injections of etanercept will be administered by the subject as a subcutaneous injection at the study site on the scheduled dose day. The subject must demonstrate to the site staff that he or she is competent to correctly administer the subcutaneous doses. Supplies of etanercept will be dispensed to subjects during the study visit.

Each dose of etanercept will consist of the complete contents of 1 SureClick autoinjector. If the first injection site occurs on the **thigh**, the second injection site should be performed on the contralateral limb. If the injection occurs in the abdomen, the first injection should be on either the right or left half of the abdomen with the second injection occurring on the opposite side of the abdomen. Each dose will follow the recommended label dosing for subjects with RA and PsA: 50 mg weekly (scheduled approximately 7 days apart). Throughout the entire study, administration of etanercept should occur on the scheduled day; however, if unavoidable, it may be given earlier or later as long as the dose is not within 3 days of the previous or next scheduled dose. If the dosing window is missed, that dose should be skipped. Etanercept is to be taken the day of a study visit in the presence of the investigator or designee.

The volume (full, partial, or none), dose date, and box number of etanercept are to be recorded on each subject's CRF.

The effects of overdose of etanercept are not known. Please refer to the US Prescribing Information or the [Etanercept Investigator's Brochure](#) for the most recent safety information.

6.3 Hepatotoxicity Stopping and Rechallenge Rules

Subjects with abnormal hepatic laboratory values (ie, alkaline phosphatase [ALP], AST, ALT, total bilirubin [TBL]) and/or international normalized ratio (INR) and/or signs/symptoms of hepatitis (as described below) may meet the criteria for withholding

or permanent discontinuation of Amgen investigational product or other protocol-required therapies as specified in the Guidance for Industry Drug-Induced Liver Injury: Premarketing Clinical Evaluation, July 2009).

6.3.1 Criteria for Permanent Discontinuation of Etanercept Due to Potential Hepatotoxicity

Etanercept should be discontinued permanently and the subject should be followed according to the recommendations in [Appendix A](#) (Additional Safety Assessment Information) for possible drug-induced liver injury (DILI), if ALL of the criteria below are met:

- TBL > 2 x ULN or INR > 1.5
- AND increased AST or ALT from the relevant baseline value as specified below:

Baseline AST or ALT value	AST or ALT elevation
< ULN	> 3 x ULN

- AND no other cause for the combination of the above laboratory abnormalities is immediately apparent; important alternative causes for elevated AST/ALT and/or TBL values include, but are not limited to:
 - hepatobiliary tract disease
 - viral hepatitis (eg, Hepatitis A/B/C/D/E, Epstein-Barr Virus, cytomegalovirus, Herpes Simplex Virus, Varicella, toxoplasmosis, and Parvovirus)
 - right sided heart failure, hypotension or any cause of hypoxia to the liver causing ischemia
 - exposure to hepatotoxic agents/drugs or hepatotoxins, including herbal and dietary supplements, plants and mushrooms
 - heritable disorders causing impaired glucuronidation (eg, Gilbert's Syndrome, Crigler-Najjar syndrome) and drugs that inhibit bilirubin glucuronidation (eg, indinavir, atazanavir)
 - alpha-one antitrypsin deficiency
 - alcoholic hepatitis
 - autoimmune hepatitis
 - Wilson's disease and hemochromatosis
 - nonalcoholic Fatty Liver Disease including Steatohepatitis
 - non-hepatic causes (eg, rhabdomylosis, hemolysis)

If an alternative cause for hepatotoxicity is identified or less stringent conditions developed than what are noted above, the investigator should determine (based on subject population and/or severity of the hepatotoxicity or event) if etanercept and other

protocol-required therapies should be withheld or permanently discontinued, as deemed appropriate for the safety of the subject.

6.3.2 Criteria for Conditional Withholding of Etanercept due to Potential Hepatotoxicity

For subjects who do not meet the criteria for permanent discontinuation of etanercept outlined above and have no underlying liver disease, and eligibility criteria requiring normal transaminases and TBL at baseline or subjects with underlying liver disease and baseline abnormal transaminases, the following rules are recommended for withholding of etanercept:

- Elevation of either AST or ALT according to the following schedule:

Baseline AST or ALT value	AST or ALT elevation
Any	> 8 × ULN at any time
Any	> 5 × ULN but < 8 × ULN for ≥ 2 weeks
Any	> 5 × ULN but < 8 × ULN and unable to adhere to enhanced monitoring schedule
Any	> 3 × ULN with clinical signs or symptoms that is consistent with hepatitis (such as right upper quadrant pain/tenderness, fever, nausea, vomiting, and jaundice).

- OR: TBL > 3 × ULN at any time
- OR: ALP > 8 × ULN at any time

Etanercept should be withheld pending investigation into alternative causes of DILI. If etanercept is withheld, the subject is to be followed according to recommendations in [Appendix A](#) for possible DILI. Rechallenge may be considered if an alternative cause for impaired liver tests (ALT, AST, ALP) and/or elevated TBL, is discovered and the laboratory abnormalities resolve to normal or baseline.

6.3.3 Criteria for Rechallenge of Etanercept After Potential Hepatotoxicity

The decision to rechallenge the subject should be discussed and agreed upon unanimously by the subject, investigator, and Amgen.

If signs or symptoms recur with rechallenge, then etanercept should be permanently discontinued. Subjects who clearly meet the criteria for permanent discontinuation should never be rechallenged.

6.4 Concomitant Therapy

Throughout the study, investigators may prescribe any concomitant medications or treatments deemed necessary to provide adequate supportive care except for those listed in [Section 6.7](#).

Concomitant therapies are to be collected from baseline (day 1) through the end of treatment.

For concomitant therapies being taken for RA and PsA, collect therapy name, indication, dose, unit, frequency, route, start date, and stop date. For other medications being taken collect therapy name, indication, start date and stop date.

6.5 Medical Devices

The following medical device, SureClick, will be used in this study and provided by Amgen. Additional details for each medical device is to be provided in the Investigational Product Instruction Manual.

6.6 Product Complaints

A product complaint is any written, electronic or oral communication that alleges deficiencies related to the identity, quality, durability, reliability, safety, effectiveness, or performance of a drug(s) or device(s) after it is released for distribution to market or clinic by either Amgen or by distributors and partners for whom Amgen manufactures the material.

This includes any drug(s), device(s) or combination product(s) provisioned and/or repackaged /modified by Amgen. Drug(s) or device(s) includes investigational product.

Concerns or irregularities about the packaging, appearance or usage of the SureClick or other Amgen provided protocol-required product (ie, etanercept) in this study are to be reported to Amgen within 24 hours of discovery or notification of the concern or irregularity.

Any product complaint(s) associated with an investigational product(s) or non-investigational product(s) or device(s) supplied by Amgen are to be reported according to the instructions provided in the Investigational Product Instruction Manual.

6.7 Excluded Treatments, Medical Devices, and/or Procedures During Study Period

Subjects are prohibited from receiving the following therapies during Treatment Phase of this study:

- Any other investigational agents
- Any commercially available biologic agent for treatment RA or PsA (other than investigational product)
- Analgesics including acetaminophen, non-steroidal anti-inflammatory drugs, hydrocodone, codeine, tramadol, propoxyphene (within 4 hours of study visit) and/or oxycodone (within 24 hours of study visit)
- Cytotoxic agents including chlorambucil, cyclophosphamide, nitrogen mustard, or other alkylating agents
- Fumarates
- Hydroxyurea
- Live vaccines (eg, measles, mumps, and rubella; varicella; intranasal flu)

6.8 Contraceptive Requirements

6.8.1 Female Subjects

Female subjects of childbearing potential must agree to use an acceptable method of contraception during treatment and for an additional 4 weeks after the last dose of etanercept.

Acceptable methods of effective contraception include: Hormonal (Combined estrogen and progestogen or progesterone-only hormonal contraception given via oral, intravaginal, transdermal, injectable, or implantable route); Intrauterine device; Intrauterine hormonal-releasing system; Bilateral tubal occlusion/ligation; Vasectomized partner (provided that partner is the sole sexual partner of the female participant who is of childbearing potential and that the vasectomized partner has received medical assessment of the surgical success); Sexual abstinence (defined as refraining from heterosexual intercourse during the entire period of risk associated with the study treatments. The reliability of sexual abstinence must be evaluated in relation to the duration of the trial and the preferred and usual lifestyle of the subject). Two barrier methods (1 by each partner) and the female partner must use spermicide (if spermicide is commercially available) with the barrier method the male must use a condom (latex or other synthetic material) and the female may select either a diaphragm, cervical cap or contraceptive sponge. A female condom is not an option because there is a risk of tearing when both partners use a condom.

Females not of childbearing potential are defined as: Any female who has had a hysterectomy, OR bilateral salpingectomy, OR bilateral oophorectomy, OR is postmenopausal. Post-menopausal females are:

- Age > 55 years with cessation of menses for 12 or more months
- Age < 55 years but no spontaneous menses for at least 2 years
- Age < 55 years and spontaneous menses within the past 1 year, but currently amenorrheic (eg, spontaneous or secondary to hysterectomy), AND with follicle-stimulating hormone levels > 40 IU/L, or postmenopausal estradiol levels < 5 ng/dL, or according to the definition of "postmenopausal range" for the laboratory involved.

If a female subject is suspected of being pregnant, the protocol-required therapies must be stopped immediately and may not be resumed until absence of pregnancy has been medically confirmed.

6.8.2 Unacceptable Methods of Birth Control for Male and Female Subjects

Birth control methods that are considered unacceptable in clinical studies include: periodic abstinence (calendar, symptothermal, postovulation methods), withdrawal (coitus interruptus), spermicides only, and lactational amenorrhea method.

7. STUDY PROCEDURES

Screening assessments and study procedures outlined in this section and in [Table 1](#) will be performed after obtaining a signed informed consent form.

It is very important to attempt to perform study procedures and obtain samples at the precise timepoints stipulated below. When it is not possible to perform the study visit at the exact timepoint, the visit may be performed within the acceptable visit window as defined in the visit-specific section below.

Any missed visits, tests not done, or examinations that are not conducted must be reported as such on the CRFs. Subsequent study visits should resume on the original schedule. Missed assessments at prior visits should not be duplicated at subsequent visits.

7.1 Schedule of Assessments

Table 1. Schedule of Assessments

	Screening	Double-blind Treatment Period		Safety Follow-up/EOS
Days	-14 to -1	1 (\pm 3 days)	8 (\pm 3 days)	38 (\pm 7 days)^a
GENERAL & SAFETY ASSESSMENTS				
Informed consent	X			
Demographic data	X			
Registration via IVR/IWR	X			
Eligibility criteria	X			
Medical history	X			
Medication history	X			
Concomitant medications	X	X	X	
Adverse events ^b	X	X	X	
Serious adverse events ^b	X	X	X	X
Physical examination ^c	X	X	X	
Vital signs	X	X	X	
Weight	X			
Height	X			
Chest x-ray (if needed) ^d	X			
LABORATORY ASSESSMENTS				
Serum pregnancy test ^e	X			
Pregnancy test (urine) ^e		X		
Hematology profile	X			
Chemistry profile	X			
Tuberculosis testing ^f	X			
Hepatitis B and C serologies ^g	X			
DOSING				
Investigational product dispensation (etanercept)		X	X	
DISEASE ASSESSMENTS				
Physician global assessment of disease activity (VAS 0-100)	X	X	X	
SUBJECT ASSESSMENTS (Reported Outcomes)				
Injection site pain (VAS 0-100)		X	X	

Footnotes defined on next page.

EOS = end-of-study, IVR = interactive voice response, IWR = interactive web response, PPD = purified protein derivative, TNF = tumor necrosis factor, VAS = Visual Analog Scale

^a Thirty days (+ 7 days) after their last dose of etanercept, subjects will be contacted by phone by the study staff to follow-up on any continuing serious adverse events and inquire about the emergence of any new serious adverse events.

^b Adverse events and serious adverse events are collected from signing the informed consent form. Adverse device effects are included in the collection of adverse events. Adverse events are collected through the end of treatment period.

^c A full physical examination will be completed at the screening visit. Subsequent physical examinations will be conducted per standard of care to monitor for any changes.

^d Only for subjects with a positive tuberculosis test (ie, positive PPD or positive or indeterminate Quantiferon).

^e For all females, unless at least 2 years postmenopausal or postmenopausal status has been confirmed or history of hysterectomy, bilateral salpingectomy, or bilateral oophorectomy.

^f Subjects will receive either a PPD test or Quantiferon test at screening. National guidelines should be followed for appropriate tuberculosis screening in the setting of anti-TNF therapy.

^g Subjects positive for hepatitis B core antibody may require additional testing for hepatitis B DNA by polymerase chain reaction.

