Analysis of covariance will be used to compare the difference in injection site pain score within subjects receiving etanercept in the currently marketed formulation and in the modified formulation, with the disease indication (RA or PsA) and the treatment as factors, adjusting for period effect and sequence effect.

[figure not shown]
Descriptive statistics for continuous variables, consists of number of observations, mean, standard error and/or standard deviation, median, 25th percentile (Q1), 75th percentile (Q3), minimum, maximum, and for categorical variables, the number of observations, frequency, and percentage will be presented. Subject disposition, demographics, baseline characteristics, and safety information will be summarized. There will be no adjustment for multiplicity and no imputation techniques for missing values. All analyses will be based on observed data.

For a full description of statistical analysis methods, please refer to [Section 10](#).

Sponsor: Amgen Inc.

Data Element Standards Version 5.0, 20 March 2015
Version(s)/Date(s):

Study Design and Treatment Schema

Abbreviations: QW = every week.

Study Glossary

Abbreviation or Term	Definition/Explanation
ALP	alkaline phosphatase
ALT	alanine aminotransferase
AST	aspartate aminotransferase
CRF	Case Report Form
DILI	drug-induced liver injury
EDC	electronic data capture
End of Follow-up	defined as when the last subject completes the last protocol-specified assessment in the study
End-of-Study (end of study)	defined as when the last subject is assessed or receives an intervention for evaluation in the study (ie, last subject completes safety follow-up)
End of Study (primary completion)	defined as when the last subject is assessed or receives an intervention for the purposes of final collection of data for the primary analysis (ie, last subject completes Study Visit 2)
End of Study for Individual Subject	defined as the last day that protocol-specified procedures are conducted for an individual subject
End of Treatment	defined as the last assessment for the protocol-specified treatment phase of the study for an individual subject
GCP	Good Clinical Practice
ICH	International Council for Harmonisation
IEC	independent ethics committee
INR	international normalized ratio
Interactive Voice Response (IVR)	telecommunication technology that is linked to a central computer in real time as an interface to collect and process information.

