7.2.3 Treatment Period

Visits will occur per the Schedule of Assessments during the treatment period from screening through week 2. Study visits may be completed within \pm 3 days of the target visit date. Prior to enrollment, subject eligibility must be confirmed with screening procedures. Subjects satisfying eligibility requirements will be enrolled. The date of the first dose of investigational product is defined as day 1. All subsequent doses and study visits will be scheduled based on the day 1 date.

The procedures completed during the 2-week treatment period are those listed in **Table 1**. Etanercept is to be administered after all assessments have been done for all visits with the exception of the VAS subject injection site pain assessment.

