7.2.4 Safety Follow-up/End-of-Study

Thirty days (+ 7 days) after their last dose of etanercept, subjects will be contacted by phone by the study staff to follow-up on any continuing serious adverse events and inquire about the emergence of any new serious adverse events.

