9.2 Safety Event Reporting Procedures

9.2.1 Adverse Events

9.2.1.1 Reporting Procedures for Adverse Events That Do Not Meet Serious Criteria

The investigator is responsible for ensuring that all adverse events observed by the investigator or reported by the subject that occur after signing of the informed consent form through the end of treatment period are reported using the Event CRF.

The investigator must assign the following adverse event attributes:

- Adverse event diagnosis or syndrome(s), if known (if not known, signs or symptoms),
- Dates of onset and resolution (if resolved),
- Severity (and/or toxicity per protocol),
- Assessment of relatedness to etanercept and SureClick device, study procedures/study activities, and
- Action taken.

The adverse event grading scale used will be the Common Toxicity Criteria. The grading scale used in this study is described in [Appendix A](#). **If the severity of an adverse event changes from the date of onset to the date of resolution, record as a single event with the worst severity on the Event CRF.**

The investigator must assess whether the adverse event is possibly related to the etanercept and SureClick device. This relationship is indicated by a “yes” or “no” response to the question: Is there a reasonable possibility that the event may have been caused by the etanercept and SureClick device?

The investigator is responsible for reviewing laboratory test results and determining whether an abnormal value in an individual study subject represents a clinically significant change from the subject's baseline values. In general, abnormal laboratory findings without clinical significance (based on the investigator's judgment) are not to be recorded as adverse events. However, laboratory value changes that require treatment or adjustment in current therapy are considered adverse events. Where applicable, clinical sequelae (not the laboratory abnormality) are to be recorded as the adverse event.

The Investigator is expected to follow reported adverse events until stabilization or reversibility.

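### No scheduled contact collects non-serious adverse events after the second injection, so period 1 and period 2 counts are gathered differently

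*Protocol*

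**What the plan says.** - **Schedule.** Table 1 (Protocol 7.1) marks adverse events at screening, Day 1 and Day 8. The Day 38 column is marked for serious events alone. Footnote b: "Adverse events are collected through the end of treatment period".
- **Order within a visit.** Protocol 7.2.3: "Etanercept is to be administered after all assessments have been done for all visits with the exception of the VAS" for injection site pain.
- **Later contact.** Under Protocol 7.2.4 and footnote a, staff telephone the subject 30 (+7) days after the last dose to "follow-up on any continuing serious adverse events and inquire about the emergence of any new serious adverse events".
- **Other routes for non-serious events.** Protocol 6.2.1.1: "Etanercept is to be taken the day of a study visit in the presence of the investigator or designee". Protocol 9.2.1.1 makes the investigator responsible for seeing that events "that occur after signing of the informed consent form through the end of treatment period are reported using the Event CRF".
- **End of the window.** The Study Glossary has End of Treatment "defined as the last assessment for the protocol-specified treatment phase of the study for an individual subject", which in Table 1 is Day 8. Protocol 7.2.3 has visits running "during the treatment period from screening through week 2", and 3.1 and 3.5.1 give a treatment period of two weeks.
- **Use of the data.** Protocol 9.1.1 plans adverse event summaries overall, by indication, by treatment arm and by period. SAP 10.7.1 allows events in the different periods to be examined when judging one formulation against the other. SAP 6 counts an event as treatment-emergent up to the end of study.

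**The concern.** Dose 1 is followed about a week later by a visit at which adverse events are collected. Dose 2 is followed by no such contact. A reaction that appears at home after dose 2 enters the database only if the subject volunteers it.

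A lower non-serious count in period 2 could then reflect weaker collection rather than fewer events. In this trial a reader could easily take it for attenuation with repeated injection, which the protocol's rationale (2.3) expects for pain. Information on non-serious reactions is also thinner than the number of injections suggests, for both formulations alike. The pain VAS and the follow-up of serious events are not touched.

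**Working it through.** The plan states no figure for adverse event capture, so there is none to reproduce. The check sets out the contacts after each dose and then illustrates the effect.

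**1. Contacts after each dose**

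| | After dose 1 (Day 1) | After dose 2 (Day 8) |
|---|---|---|
| Dosing watched on site | yes | yes |
| Next visit with an adverse event mark | Day 8, before dose 2 | none |
| Days to that visit | 8 - 1 = 7 (4 to 10 with the ±3 window) | not applicable |
| Later call | not applicable | 30 to 37 days after dose 2, serious events only |

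Expected injections are 112 first and 2 × 53 = 106 second (56 × 0.95 = 53.2 per sequence), so 218 in all. A scheduled non-serious collection follows at most 112/218 = 51% of them.

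**2. Length of the window after a Day 8 dose**

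- Glossary reading: the window ends with the Day 8 assessment, so 8 - 8 = 0 days.
- Two-week reading, ending Day 14: 14 - 8 = 6 days.

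**3. Illustration**

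Let p be the risk per injection of a non-serious event arising after the subject leaves the site, and c the share of those recorded after dose 2 relative to dose 1. The documents give neither, so both are assumptions. Risk is taken as equal in both periods and for both formulations, with full capture after dose 1.

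- Period 1 cases = 112p; period 2 cases = 106pc.
- Cases per formulation = 56p + 53pc.
- Share lost per formulation = 53(1 - c)/109, which does not depend on p.

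At p = 10%:

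| c | Period 1 | Period 2 | Per formulation | Lost |
|---|---|---|---|---|
| 100% | 11.2 | 10.6 | 10.9 | 0% |
| 75% | 11.2 | 8.0 | 9.6 | 12% |
| 50% | 11.2 | 5.3 | 8.3 | 24% |
| 25% | 11.2 | 2.7 | 6.9 | 36% |

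With c = 50%, p = 5% gives 5.6 against 2.7, and p = 20% gives 22.4 against 10.6. Apart from dropout, the period 2 to period 1 ratio is simply c, with no true period effect.

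**4. Formulation comparison**

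Each formulation supplies 56 first and 53 second injections, so the same factor, (56 + 53c)/109, multiplies both pooled rates. Their ratio is unchanged. An absolute risk difference shrinks to that fraction, 82.5/109 = 76% at c = 50%.

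**The case against.** Several counter-arguments have weight.

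- **Nothing in the text says that subjects are questioned after dose 1.** Protocol 7.3.9 and 9.2.1.1 speak, for both periods, of what the investigator sees or the subject reports. This stands. The documented difference is a scheduled visit against none, not prompted against unprompted questioning.
- **Immediate reactions are caught in both periods.** Dosing is witnessed, and footnote b brings device effects into adverse event collection. This stands, and limits the gap to events arising off site.
- **Reportability depends on when the event occurred.** A non-serious event within the window that is mentioned on the later call can still be entered. This also stands, but nobody is told to ask.
- **The follow-up may itself be a collection visit.** The synopsis calls it a visit, and 7.3.9 has events collected at every study visit. This does not carry: Table 1, footnotes a and b, and 7.2.4 all make it a call about serious events.

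A reader might also infer more than the documents support:

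- *Events after dose 2 go uncollected.* They do not, because the on-site and volunteered routes remain.
- *The formulation safety comparison is biased.* Balanced sequences prevent that unless capture depends on formulation. Within a single sequence, equal formulations at c = 50% would show modified-to-current ratios of 0.5 (AB) and 2.0 (BA), but no section plans that contrast. SAP 10.7.1 says only that events by period may be examined.
- *The treatment-emergent window has no end for an individual.* SAP 6 defines end of study by the last subject, but the protocol glossary also defines it per subject.

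**Conclusion.** The point holds and is minor. No scheduled contact collects non-serious events after dose 2, and the two descriptions of when treatment ends leave either 0 or 6 days of collection after a Day 8 dose. Contrasts of period 1 with period 2 are therefore confounded with collection method. Formulation comparisons within a period or pooled are not shifted towards either product, provided that capture is unrelated to formulation, but they rest on fewer recorded events.

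The existence of the gap follows from the schedule alone. Its size does not: 11.2 against 5.3 cases and the 24% loss rest wholly on the assumed 10% off-site risk, full capture after dose 1 and 50% relative capture after dose 2. The loss ranges from 12% to 36% as relative capture goes from 75% to 25%.

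**What to change.** 1. On the safety call already planned, also ask about non-serious events after dose 2, at least injection site reactions, with onset dates. Ask whether and when commercial etanercept was started, since 3.1 allows it and 6.4 stops collecting concomitant therapy at the end of treatment. Carry this into Table 1, footnotes a and b, 7.2.4 and 9.2.1.1.
2. Define the end of the treatment period once, per subject. Extend the non-serious collection window to match, and align the SAP treatment-emergent window with it.
3. In SAP 10.7.1, tabulate non-serious events by formulation within period and pooled, using the same post-injection window for both doses. One option is 7 days, cut for both doses to the subject's own dosing interval where that is shorter. Protocol 6.2.1.1 lists a dose date but no dose time, so state a convention for events starting on the day of dose 2. Add a caveat that period differences may reflect collection method and recall.

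**Cost.** A few questions on an existing call, slightly more data entry, and a protocol amendment, which under 12.1 needs ethics approval and a signed investigator page at each of about 30 sites. Recall would be 30 to 37 days by phone for dose 2 against about 7 days in person for dose 1. The call reduces under-collection but does not make the periods fully comparable, so the caveat stays. If the call is left as it is, items 2 and 3 are still worth making.

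As a separate editorial matter, reconcile the synopsis's follow-up visit with the phone call. Also reconcile Day 38 (±7) in Table 1 (23 to 37 days after a Day 8 dose) with the 30 (+7) days in footnote a and 7.2.4.
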